| Study Design | Prospective, randomized, multi-center, comparative effectiveness trial; patients randomized with equal allocation (1:1). Baseline and peri-procedural data collection will be partially extracted from the Society of Thoracic Surgeons (STS) Data Registry. Limited additional data will be collected to assess coronary anatomy, pharmacology specific to the procedure, device usage, etc. When allowed by local IRB/REBs, follow-up data collection, with the exception of data collection at post-intervention clinical visits, will be collected centrally via phone follow-up by the Hybrid Trial Data Coordinating Center (DCC), and will focus on patient-reported MACCE and QOL, supplemented by limited supporting documentation to verify MACCE events, and cost data collected from the University Health Consortium (UHC) and directly from hospitals for non-UHC members. All MACCE events will be adjudicated by a Clinical Events Committee (CEC). The estimated enrollment period is 24 months and all patients (n = 2354) will be followed for 5 years following randomization. |
| Target Population | Patients with multi-vessel CAD involving the LAD distribution with a clinical indication for revascularization and eligible for both HCR and multi-vessel PCI with DES. |
| Rx arms | 
 ○ HCR with sternal-sparing, off-pump Left Internal Mammary Artery (LIMA) to LAD + PCI with metallic drug eluting stents (DES) of non-LAD vessels ○ Multi-vessel PCI with metallic DES, including the LAD and or LM. |
| Sample Size | 2354 patients; assuming an estimated event rate of approximately 25% in the PCI group at 5 years; 0.05 type I error (2-sided) and assuming: (a) minimum follow-up of 5 years, (b) 80% power, (c) drop-in and drop-out rates of approximately 0.5% and 2% respectively, annually, and (d) 15% loss to follow-up by end of the study, 530 events will need to be observed (or 2354 patients) to detect a relative decrease in MACCE of $\geq 20\%$ in the HCR compared to the PCI group. Estimates of loss to follow-up, and cross-over rates are conservative and justify fixing the power at 80%. |
| Duration | Accrual over 2 years; accrual will terminate when 530 events have occurred or 2354 patients are randomized, whichever comes first. All patients will be followed for 5-years. |

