For patients identified in the setting of a 3-vessel qualifying diagnostic angiogram and successful PCI of a non-LM or non-LAD vessels in the same or subsequent procedure, randomization into the trial must occur within 90 days following the initial qualifying angiogram. The first “study” intervention must be performed within 14 days following randomization (see above Table for possible procedure options).

Randomization will be stratified by center, PCI of non-LM or non-LAD vessels within the prior 90 days, and type of vessels treated (1) LAD and Diagonal only; 2) LAD (or Left Main) and LCX or RCA; 3) LAD (or Left Main) and both LCX and RCA). The randomization scheme will be in random blocks of 4 and 6 within each stratum to maintain balance.

Randomization will be generated centrally and performed through a Web-based data collection system that automates the delivery of the randomization codes. The treatment assignment will be

sent to the site coordinator electronically, in a secure fashion, and electronic verification of the treatment assignment will be required before proceeding with the treatment intervention. From that point on, primary efficacy will be analyzed by intention-to-treat; that is, the patients will be grouped by their assignment at randomization whether or not they actually received the treatment to which they were assigned.

MASKING

Neither patients nor investigators will be blinded to treatment assignment due to the nature of treatment interventions. Clinical and CCC investigators will, however, be blinded to all data from other clinical sites, except serious unexpected adverse events (SAEs) for IRB/REB reporting purposes. The DCC Research Nurse will be blinded to treatment assignment during follow-up telephone calls and will be blinded to aggregate outcomes data. MACCE events will be adjudicated by the independent CEC and trial oversight will be provided by an independent Data & Safety Monitoring Board (DSMB).

TREATMENT INTERVENTIONS

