Data extracted from UHC database and UB forms for all hospitalizations required to complete the original planned revascularization strategy (if staged)

Medical costs are defined as hospital costs and physician fees incurred during the index revascularization procedure(s) and hospitalization. Cost data will be extracted from the UHC operational database system for member sites, and from UB medical claims forms for sites without UHC membership. Dates of charges and revenue codes will be used to match the cost data with data on study-procedure related hospitalization from the STS registry. UB medical claims will be converted to costs using the same methodology as used by UHC to estimate costs including center-specific ratios of cost to charges. These ratios will be based on the annual Medicare costs reports submitted annually by participating study sites to Medicare. Physician fees will be based on collected length of stay data and the Medicare fee schedule. Physician fees for HCR and PCI procedures will include those for the primary surgeon, surgical assistant, and anesthesiologist. Non procedure-related physician fees regarding the index hospitalization(s) will be based on collected length of stay data and the Medicare fee schedule. The patient-specific cost data downloaded from the UHC operational database system and electronic UB data will be de-identified and coded with the unique study ID, and subsequently transferred by the participating clinical site to the DCC via a secure FTP website.

Post-Intervention Site Activities

Follow-up must be performed at 30 (± 7) days following all procedures (index and staged) that occur within 90 days of the first study revascularization procedure.. However, if a staged procedure occurs <45 days after the first procedure, it will not be considered a protocol violation if a 30-day follow-up visit was not performed after the first procedure.

Medications

This form captures medication use, including antiplatelet and anticoagulant agents, beta blocker, and ACE inhibitors, ARBs, aldosterone antagonists and statins.

Angina Class - Canadian Cardiovascular Society Classification (CCSC)

The presence of angina will be assessed, and when present, classified according to the CCSC

Quality of Life

The SF-12 and EuroQol (Appendix II) questionnaires will be completed by the patient to assess quality of life.

MACCE and Other Cardiovascular and Bleeding Events

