Information regarding MACCE, other cardiovascular and bleeding events will be recorded. Limited source documentation pertaining to the MACCE event will be collected and uploaded into the EDC as detailed in the trial Manual of Procedures (MOP).

Long-term Patient-Reported MACCE & QoL***MACCE and Other Cardiovascular and Bleeding Events***

Follow-up must be performed at 6 (± 1), 12 (± 1), 18 (± 1), 24 (± 1), 30 (± 1), 36 (± 1), 42(± 1), 48 (± 1), 54 (± 1), and 60 (± 1) months post-randomization, via centralized DCC telephone follow-up (when allowed by local IRB/REBs)

Follow-up MACCE and other cardiovascular and bleeding event assessments will be conducted via telephone contact with patients by the DCC research nurse. Site coordinators will conduct follow-up via telephone at sites where the IRB/REB does not approve of centralized DCC follow-up. Vital status and the occurrence of any MACCE and other cardiovascular and bleeding event events since the last follow-up will be ascertained.

Information regarding MACCE and other cardiovascular and bleeding event events will be recorded by the DCC research nurse or local site coordinator. In addition, limited source documentation pertaining to the MACCE and selected other cardiovascular events will be collected by the site coordinator and uploaded into the EDC for review by the Clinical Events Committee.

For patients who have completed their planned revascularization procedure(s) as documented on the Planned Revascularization form, including planned staged procedures, any subsequent PCI or CABG performed will be considered an unplanned revascularization, and treated as a MACCE event. As noted in the Definition and Measurement of Endpoints section, this excludes an additional planned staged revascularization if it is declared by the end of the prior planned study intervention procedure.

Medications

At 6 (± 1), 12 (± 1), 18 (± 1), 24 (± 1), 30 (± 1), 36 (± 1), 42(± 1), 48 (± 1), 54 (± 1), and 60 (± 1) months post-randomization, via centralized DCC telephone follow-up (when allowed by local IRB/REBs)

Patient reported medication use since the last follow-up, specifically, antiplatelet and anticoagulant agents, beta blocker, ACE inhibitors, ARB, aldosterone antagonists and statin use will be recorded by the DCC research nurse or local site coordinator.

Angina Class - Canadian Cardiovascular Society Classification (CCSC)

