At 6 (± 1), 12 (± 1), 18 (± 1), 24 (± 1), 30 (± 1), 36 (± 1), 42(± 1), 48 (± 1), 54 (± 1), and 60 (± 1) months post-randomization, via centralized DCC telephone follow-up (when allowed by local

The presence of angina will be assessed by the DCC research nurse, and when present, classified according to the CCSC scale and documented on this form. CCSC classification scheme is detailed in Appendix I.

Quality of Life

At 12 (±1), 24 (±1), 36(±1), 48 (±1), and 60 (±1) months post-randomization, via centralized DCC telephone follow- up (when allowed by local IRB/REBs)

The SF-12 and EuroQoL will be administered annually, either by phone from the DCC research nurse or site coordinator, or via electronic patient portals, including electronic QoL surveys that can be utilized for all patients with computer, tablet or smart phone capability. The electronic forms will also be accessible for patient reporting via a password protected portal on the HCR Trial website.

Costs

Collected at 12 (±1), 24 (±1), 36 (±1), 48 (±1), and 60 (±1) months post-randomization, via electronic transfer from UHC database and UB forms

Medical costs were defined as hospital costs, physician fees, outpatient procedure costs, the cost of prescription drugs, and the cost of rehabilitation incurred after the index hospitalization. Medical claims associated with any hospital stay and outpatient service in participating sites are collected annually. Cost data will be extracted from the UHC operational database system for member sites, and from UB medical claims forms for sites without UHC membership. UB medical claims will be converted to costs using the same methodology as used by UHC to estimate costs using center-specific ratios of cost to charges. These ratios will be based on the annual Medicare costs reports submitted by participating study sites to Medicare. Multivariable imputation algorithms will be used to impute costs for patient-reported out of network hospital stays. Physician fees will be based on collected MACCE and length of stay data and the Medicare fee schedule. Resource use associated with prescribed medication and the rehabilitation of myocardial infarction and stroke will be estimated based on patient-reported information and will be converted into dollars using reimbursements from Centers for Medicare and Medicaid Services costing reports

Event Driven Data Collection

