Sample size for this study was determined based on the following operating characteristics: (a) two sided type I error fixed at 0.05, (b) 80% power, (c) minimum follow-up of 5 years, 2-year enrollment period with uniform enrollment (d) 5-year MACCE rate in the PCI group of approximately 25%, (e) expected 5-year MACCE relative rate reduction in the HCR group of $\geq 20\%$, (f) drop-in (HCR to PCI) and drop-out (PCI to HCR) rates of approximately 0.5% and 2% respectively, and (g) loss to follow-up by the end of the study of 15%. Under the above assumptions it is estimated that 530 events (or 2354 patients) will be required to detect a relative decrease in MACCE of $\geq 20\%$ in the HCR compared to the PCI group. This is a reasonable improvement based on estimates from recent studies.²⁵⁻²⁸

Interim Monitoring Guidelines

The objectives of interim monitoring are to (1) monitor for safety, (2) track participant accrual rates, and (3) monitor the primary and secondary outcomes for early evidence of efficacy, harm or futility. To accomplish this, summaries of data quality, accrual, adherence, distribution of

baseline factors, safety, study endpoints and other analyses as requested will be prepared for review by the DSMB. A single interim analysis and one final analysis are planned for this trial, for a total of two analyses. The interim analysis will be conducted when 0.5 fraction of the total number of events have been observed. This interim analysis will evaluate the composite rate of adjudicated death, stroke or MI (excluding unplanned repeat revascularization), as the endpoint is being conducted for safety, rather than efficacy, purposes. We will use an alpha-spending O'Brien-Fleming sequential procedure as a guideline for decision-making. At the interim analysis the value of the test statistic will be compared with the alpha spending function critical value. The p-values for the interim monitoring analysis and the final analysis are, 0.0031, and 0.05, respectively.

Stopping Rule

We do not anticipate stopping the trial for evidence of early efficacy or futility at the time of the interim analysis. The collection of 5-year follow-up information on all patients enrolled in the trial is necessary to provide a comprehensive overview of the relative safety and effectiveness of the two randomized strategies.

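### After the 30-day visits MACCE is detected mainly by asking the patient; the participating-site claims collected each year for cost are not used to look for unreported events

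*Combined protocol and SAP*

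**What the plan says.** The Abstract (Study Design) states that follow-up "will focus on patient-reported MACCE and QOL, supplemented by limited supporting documentation to verify MACCE events". The footnote to the Data Collection Schedule says that registry data stop 30 days after the index intervention and that MACCE is collected by telephone from then on.

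Under Long-term Patient-Reported MACCE & QoL, the Data Coordinating Center (DCC) nurse calls the patient every 6 months and asks about vital status and any MACCE. The exception is: "Site coordinators will conduct follow-up via telephone at sites where the IRB/REB does not approve of centralized DCC follow-up". Event Driven Data Collection adds reports that the patient makes by telephone or portal between calls. Site coordinators then collect limited source documents, and the Clinical Events Committee (CEC) adjudicates.

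On masking: "Neither patients nor investigators will be blinded to treatment assignment due to the nature of treatment interventions". The DCC nurse is masked during calls. No masking is stated for a site coordinator who makes them.

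On claims, the Costs section says: "Medical claims associated with any hospital stay and outpatient service in participating sites are collected annually". For the index stay, Index Hospital Costs says: "Dates of charges and revenue codes will be used to match the cost data with data on study-procedure related hospitalization from the STS registry". The same section has the cost data coded with the study ID and transferred to the DCC. Informed Consent covers release of billing information for all hospitalizations and outpatient services, including to the DCC.

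**The concern.** Verification works in one direction. Source documents and adjudication can reject a reported event that was not real, but they cannot recover one that nobody reported. Under Analysis of Primary Endpoint, a patient alive and free of recorded MACCE is censored. An unreported infarction, stroke or revascularization therefore counts as event-free time unless a later event is recorded.

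Two things are at stake. Equal loss in both arms costs events and therefore power. Unequal loss biases the treatment comparison, and patients here know their assignment. The plan contains no measure of reporting completeness, overall or by arm, so neither problem would be visible. Meanwhile a second, independent record of hospital stays at participating sites is already to be collected every year.

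**Working it through.** **Inputs.** From Power and Sample Size: "two sided type I error fixed at 0.05"; 80% power; "5-year MACCE rate in the PCI group of approximately 25" per cent; "expected 5-year MACCE relative rate reduction in the HCR group of" at least 20%; 530 events or 2354 patients. The documents give no sensitivity for patient report and no fatal/non-fatal split of first events. The shares used in steps 3 and 4 are assumptions.

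**1. The plan's own figures.** The mean 5-year risk is (0.25 + 0.20)/2 = 0.225, and 2354 × 0.225 = 529.65, which is the stated 530. A multi-state log-rank calculation gives N = 2355 against the stated 2354. It uses constant hazards from 25% and 20% at 5 years, uniform 2-year accrual, 5 to 7 years of follow-up, crossover of 0.5% and 2% a year, and 15% loss. It expects about 568 events rather than 530, so step 3 is checked under both.

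**2. Effect implied by 530 events at 80% power.** |ln HR| = 2 × (1.960 + 0.8416)/√530 = 0.2434, so HR = 0.784. The undiluted HR from the two risks is ln 0.80/ln 0.75 = 0.776.

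**3. Equal loss in both arms.** Events D = 530 × (1 − non-fatal share × missed share). Power = Φ(0.2434 × √D/2 − 1.96).

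| Non-fatal share of first events | Missed share of those | D | Power |
|---|---|---|---|
| 70% | 5% | 511 | 79% |
| 80% | 10% | 488 | 77% |
| 90% | 15% | 458 | 74% |

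The multi-state model, with detection of all events set at 95%, 90% and 85%, gives 78.2%, 76.3% and 74.2%. The average HR stays at about 0.79, so equal loss costs power and hardly moves the estimate.

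**4. Unequal loss.** Assume 80% of first events are non-fatal, with reporting sensitivity of 90% in one arm and 95% in the other.
- HCR 90%, PCI 95%: 0.20 × (0.2 + 0.8 × 0.90) = 0.184; 0.25 × (0.2 + 0.8 × 0.95) = 0.240; observed risk ratio 0.77.
- Reversed: 0.192/0.230 = 0.83.

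The true ratio is 0.80 in both cases. With no true effect, and detection of all events at 100% against 95%, the multi-state model has about 613 events and an apparent HR of 0.95. Then |ln 0.95| × √613/2 = 0.635, and the two-sided rejection rate is Φ(0.635 − 1.96) + Φ(−0.635 − 1.96) = 0.093 + 0.005, about 9.7% instead of 5%.

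**5. Why these are upper figures.** Steps 3 and 4 apply the missed share to events at any time. Early events have other routes: biomarkers and an ECG around every procedure (Treatment Interventions), site and registry capture during procedural hospitalizations, and site follow-up 30 days after each procedure done within 90 days of the first.

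**6. Stated uses of claims.** Index Hospital Costs, Costs, and Cost-effectiveness each use claims to estimate cost. No section compares claims with reported MACCE.

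**The case against.** The strongest reply is that follow-up is active and reasonably protected. Patients are called every 6 months, by default by a masked nurse, and vital status is ascertained at each call. Re-hospitalizations are recorded as an outcome of their own, so a patient who mentions a stay without recognising an infarction can still bring the event to light. Monitoring focuses partly on study endpoints and allows remote access to medical records. The trial is deliberately large and simple, and details of event documentation are left to a Manual of Procedures that is not part of the documents.

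This stands as mitigation. It does not close the gap: the re-hospitalization route still starts with the patient, and monitoring is not described as a search for unreported events.

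A reader might infer that the DCC already holds every patient's hospital claims, and that late MACCE is found only if the patient volunteers it. The documents support neither. Annual claims cover participating sites only, and out-of-network stays are themselves patient-reported. The trial allows non-U.S. sites, and claims are not shown to exist for their patients. Study-ID coding and transfer to the DCC are stated under index costs and not repeated for annual costs. The only matching fields named are charge dates and revenue codes, so diagnosis codes in the extract cannot be assumed.

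**Conclusion.** The point holds as a gap in ascertainment that is cheap to narrow. Long-term detection of non-fatal MACCE rests mainly on asking the patient, nothing described searches for what is not reported, and an available partial cross-check is used only for cost.

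Its size is unknown. If 70-90% of first events are non-fatal and 5-15% of those are missed equally in both arms, power falls from 80% to about 79-74%, as an upper range. It would be tempting to conclude that the primary result will be biased. The documents do not support that: bias needs completeness to differ by arm, no figure or mechanism in the plan establishes such a difference, and its direction cannot be determined. What can be said is that a modest difference would matter and that the plan could not reveal it.

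**What to change.** Add to Data Collection:

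*Each year, DCC staff other than the masked telephone nurse will match participating-site claims, by study ID, to reported hospitalizations and MACCE. Any unmatched inpatient stay, and any unmatched revascularization, MI or stroke code where the extract carries such codes, triggers a source-document request and CEC review. The same rule applies in both arms. The number of unmatched events is reported by arm.*

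Also state that the annual claims carry the study ID and go to the DCC, as Index Hospital Costs already says for index costs. The inpatient-stay trigger can work from stay dates, so it does not depend on diagnosis codes. Keep patient report as the trigger for out-of-network stays and for sites without University HealthSystem Consortium or Uniform Billing claims.

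The cost is protocol wording, a yearly matching step on data already planned and consented, and some extra document requests and adjudications. Coverage is partial. In return, the by-arm count gives the trial an internal check on reporting completeness.

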We plan to enroll 2354 patients in the Hybrid Coronary Revascularization Trial through active screening and recruitment by the multidisciplinary Heart Teams at the clinical sites. The strategies used to successfully enroll this trial will build on the momentum achieved over the last several years in the formation of Heart Teams at participating hospitals, consisting of interventional cardiologists and surgeons who work collaboratively to provide unified treatment recommendations for patients with complex CAD and valvular heart disease. The strategies will include: frequent presentations by the site Principal Investigators regarding the trial in weekly interventional cardiology and cardiac surgery conferences, as well as the combined multi-

disciplinary conferences; review of consecutive patients with multi-vessel disease by the site participating Heart Teams prior to recommending treatment options; regular Grand Rounds presentations at clinical sites as well as referring hospitals, mailings to referring physicians of the study hospitals, symposia and health care events targeted towards this population; as well as telephone calls to neighboring health care facilities. The DCC will regularly assess actual enrollment in relation to pre-specified goals, and additional interventions directed by the Clinical Coordinating Center (CCC) to increase enrollment, will be implemented as needed. The Pre-Screening Failure Form will identify numbers of patients screened and reasons for non-enrollment in the study.

Inclusion of Women and Minorities

The inclusion of women and minorities in clinical trials is critical for scientific, ethical, social reasons, and for the generalizability of trial results. The Hybrid Trial investigators are strongly committed to ensuring a balanced recruitment of patients regardless of sex or ethnicity, and intend to recruit at least 30% women and 25% minorities. The following measures will be employed to ensure adequate representation of these groups: (1) documentation of the number of women and minorities screened and enrolled via screening/exclusion logs; (2) monitoring of such logs from each clinical center on a regular basis; and (3) if necessary, the development and implementation of additional outreach programs designed to recruit adequate numbers of women or minorities.

TREATMENT ASSIGNMENTS

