All patients enrolled in this trial will undergo coronary artery revascularization. Patients will be randomly assigned to the following treatment groups:

Hybrid Coronary Revascularization (HCR Group)

LIMA to LAD + PCI with metallic DES of non-LAD vessel(s)

Multi-vessel PCI (PCI-only Group)

Multi-vessel PCI with metallic DES, including the LAD and or LM

| Qualifying angiogram type | Time from the 3-vessel qualifying angiogram until randomization | Time from randomization to 1 st procedure | Sequence options if randomized to HCR | Sequence options if randomized to multi-vessel PCI | If staged: Time from first revascularization intervention after randomization until final planned revascularization intervention |
|--|---|--|---|--|--|
| 3-vessel angiogram only (PCI not performed) | Anytime within 90 days | ≤14 days after randomization | 
 1. Off-pump minimally invasive CABG first followed by staged PCI (recommended) 2. PCI first followed by staged Off-pump minimally invasive CABG 3. Concomitant Off-pump minimally invasive CABG and PCI (same calendar day) | 
 1. Single procedure multi-vessel PCI 2. Staged PCI procedures | No longer than 90 days (≤60 days recommended) |
| 3-vessel angiogram followed by PCI of a non-LM or non-LAD lesion in the same or subsequent procedure within 90 days prior to randomization | Anytime within 90 days | ≤14 days post randomization | 
 1. If only untreated LM or LAD lesion remains: Off-pump minimally invasive CABG 2. If non-LM or non-LAD lesion(s) remain: Same 3 options as above | 
 1. If only untreated LM or LAD lesion remains: single PCI procedure 2. If non-LM or non-LAD lesion(s) remain: Same 2 options as above | No longer than 90 days (≤60 days recommended) |

Patients will be randomly assigned (1:1) to HCR or multi-vessel PCI. The randomization procedure will be performed after patient eligibility is confirmed.

For patients identified in the setting of a qualifying 3-vessel diagnostic angiogram without a PCI performed during or subsequent to the diagnostic angiogram, randomization must occur within 90 days following the qualifying angiogram. The first study revascularization intervention is recommended to be performed within 72 hours post randomization and must be performed within 14 days following randomization (see above Table for possible procedure options).

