The study will be conducted in between 50 and 125 U.S. and non-U.S. clinical sites with extensive experience in minimally invasive surgical coronary revascularization and multi-vessel PCI, as well as expertise in hybrid revascularization. The sites will be selected by the multi-disciplinary Hybrid Trial Steering Committee with particular focus on procedural expertise and evidence of a functioning multi-disciplinary heart team. An average recruitment of 98 patients monthly (2 patients/month/site) is anticipated.

Each clinical center will be required to obtain IRB/REB approval for the initial protocol and informed consent document and any subsequent revisions in a timely fashion, to recruit patients, to collect data and enter it accurately into the electronic data capture (EDC) system, to faithfully follow the protocol and adhere to the standards of Good Clinical Practice (GCP) and HIPAA or Personal Information Protection and Electronic Documents Act (PIPEDA) regulations. In addition, centers will be required to provide the DCC the information necessary for interim, annual, and final reports, to provide source documents, data and regulatory documents to study monitors, to respond promptly to DCC inquiries, and, to participate in analyses and reporting of study results.

Site Approval

The following documents are required for all sites approved to participate in the trial:

- Clinical Study Agreement with the CTSN DCC: InCHOIR, Department of Health Policy, Icahn School of Medicine at Mount Sinai
- Signed Conflict of Interest Statements
- Signed and dated CVs for all staff on Delegation of Authority Log
- Completed Delegation of Authority Log
- HIPAA/PIPEDA and Human Subjects/GCP training documentation (as required by local institutional guidelines) for all staff on Delegation of Authority Log
- Current licenses for all staff on Delegation of Authority Log
- IRB/REB roster
- IRB/REB approval for protocol, informed consent document, HIPAA authorization (US sites)
- NIH Stroke Scale Training Certification for appropriate staff
- Laboratory Normal Ranges
- Certification forms for Surgeons and Interventional Cardiologists
- Signed Document Approval Form for protocol
- Study-specific training documents

INVESTIGATORS

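### Open-label trial with blocks of 4 and 6 inside center-level cells: a site could guess about 62-67% of next assignments, and printing the sizes lets it call roughly a quarter with high confidence

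*Combined protocol and SAP*

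**What the plan says.** All quotes are from the combined protocol and SAP.

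- **Treatment Assignments:** "Patients will be randomly assigned (1:1) to HCR or multi-vessel PCI". "Randomization will be stratified by center, PCI of non-LM or non-LAD vessels within the prior 90 days, and type of vessels treated", the last factor having three levels. "The randomization scheme will be in random blocks of 4 and 6 within each stratum to maintain balance". The list is generated centrally, and codes are released by a web system after eligibility is confirmed.
- **Masking:** "Neither patients nor investigators will be blinded to treatment assignment due to the nature of treatment interventions". Clinical investigators are blinded to data from other sites, but not to their own site's assignments.
- **Timing (Treatment Assignments):** for patients without a prior PCI, "randomization must occur within 90 days following the qualifying angiogram". The same 90 days apply to patients who have had a non-LM, non-LAD PCI.
- **Size (Recruitment Strategies, Clinical Centers):** "We plan to enroll 2354 patients in the Hybrid Coronary Revascularization Trial"; "The study will be conducted in between 50 and 125 U.S. and non-U.S. clinical sites"; "An average recruitment of 98 patients monthly (2 patients/month/site) is anticipated".

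The documents say nothing about how predictable the next assignment is, or about keeping block sizes from sites. Each site must sign a document approval form for the protocol, so each site holds the page that gives the sizes.

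**The concern.** A permuted block must end in balance, so past assignments in a block carry information about the next one. Here the site sees every past assignment, knows the candidate's cell before randomizing (the revascularization plan for both arms is recorded first), and knows the only two block lengths. The site also judges suitability for both arms and likely compliance, and chooses when within 90 days to randomize. Central web release hides the list but does not prevent inference from what the site has already seen.

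If a site acted on such inference, for example by deferring a higher-risk patient when surgery looked likely, the arms would differ in risk before treatment. Intention-to-treat analysis preserves that difference. The stratified log-rank test and the Cox model, which adjust only for the stratification factors, would not remove it from the MACCE comparison.

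**Working it through.** The plan gives no predictability figure, so there is none to reproduce.

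**Inputs from the protocol.** Block sizes 4 and 6, 1:1 allocation; 2 × 3 = 6 cells per center; 2354 patients; 50 to 125 sites. That is 300 to 750 cells, or 2354/300 = 7.8 down to 2354/750 = 3.1 patients per cell on average. The stated recruitment rate implies 98/2 = 49 sites, close to the lower end.

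**Assumptions.** The two sizes are equally likely. The number of patients per cell is Poisson with six equal cells (skewed mixes were also tried). The site tracks every cell and always guesses.

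**Step 1: start of a block.** The chance that the first two are both a given arm is (2/4)(1/3) = 1/6 for size 4 and (3/6)(2/5) = 1/5 for size 6. The opposite arm then follows with probability 1 or 3/4. So after two alike,

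P(opposite next) = (1/6 × 1 + 1/5 × 3/4) / (1/6 + 1/5) = 0.3167/0.3667 = 0.864.

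After three alike at the start of a block it is 1.

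**Step 2: best guess over the first four patients in a cell.**
- Patient 1: 0.50.
- Patient 2: average of 2/3 and 3/5 = 0.633.
- Patient 3: 0.367 × 0.864 + 0.633 × 0.5 = 0.633.
- Patient 4: 0.5 × 1 + 0.5 × (0.1 × 1 + 0.9 × 2/3) = 0.85.

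Cumulative: (0.50 + 0.633 + 0.633 + 0.85)/4 = 65.4%. Continuing the enumeration gives 67.2% at 6 patients, 66.8% at 8 and 68.0% at 12.

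**Step 3: averaged over the planned trial, with the share of assignments that can be called confidently.**

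| | 50 sites | 125 sites |
|---|---|---|
| Best guess using the sizes | 66.6% | 62.3% |
| Same, skewed cells | 66.8-67.0% | 63.8-64.4% |
| Naming whichever arm is behind (sizes not used) | 66.6% | 62.3% |
| Callable with at least 80% certainty, sizes known | 28-29% | about 22% |
| Callable with full certainty, sizes known | 5-6% | about 3% |

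Rows 1 and 3 agree: knowing the sizes does not raise the average. It raises confidence. If sites did not know the sizes (assumed beliefs: 2 to 8, or 4 to 10), the share callable at 80% or more falls to about 5-12% at 50 sites and to as little as 1% at 125 sites. Full certainty falls to zero.

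**Step 4: alternatives (guess right at 50 / 125 sites, same cells).** Blocks 4, 6, 8: 65.1% / 60.4%. Blocks 6, 8, 10: 62.8% / 57.2%.

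**Step 5: a worst case for the test.** None of these inputs is in the documents except the 530 events. Suppose half the patients have 30% and half 15% five-year risk, and every site shifts the high-risk share by 5 to 15 points in the same direction whenever it holds a guess. With no true effect the hazard ratio would be about 0.975 to 0.927. With z = |ln HR| × √530 / 2, z runs from 0.29 to 0.87. The two-sided rejection rate, P(Z > 1.96 − z) + P(Z < −1.96 − z), runs from 6% to 14%.

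**The case against.** Center-stratified blocks of varying size with central release are a deliberate choice, made for balance, and center balance has real value when the procedures depend on the operator. The protocol also has safeguards beyond the web system:

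- an interventional cardiologist and a surgeon must agree on suitability for both arms;
- Heart Teams review consecutive multivessel patients;
- an eligibility checklist is signed, and plans for both arms are recorded before randomization;
- patients not enrolled are logged with a reason;
- the clinical coordinating center monitors whether enrollment is appropriate.

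Much of this stands: selection is constrained and partly visible. The safeguards do not close the gap, because deferring or declining a candidate happens before eligibility is confirmed. The screening form is described as recording quarter, year, age, gender, race and reason. It lists no exact date or cell, so it could not readily be lined up with the allocation sequence.

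Two stronger readings are tempting, and the documents support neither. A reader might infer that printing the sizes is what makes two thirds of assignments guessable. The guess that ignores the sizes scores the same, and two thirds is the upper end of the site range. A reader might also infer that the false-positive rate will reach 14%. No document gives those risks or any selective behaviour, and sites favouring opposite arms would cancel. If only half the sites acted, and only on guesses of at least 80% certainty, the same formula gives 5.1-6.0%.

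**Conclusion.** The point holds as an avoidable exposure, not as evidence of bias. Small blocks inside center-level cells of an unmasked trial give a site that keeps track a gain of about 12 to 17 percentage points over chance. Disclosure gives it confidence in roughly a quarter of its calls. The size rests on the equal size mix, on roughly Poisson cell counts and on a site that tracks all its cells. The comparison with undisclosed sizes also rests on what sites are assumed to believe. How far any of this would reach the MACCE result cannot be settled from the documents.

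**What to change.** **Recommended.** Remove the block sizes from the protocol and hold them in a restricted randomization document at the data coordinating center. Because 4 and 6 are already known, generate a new list with a different, undisclosed set of varied sizes for patients not yet randomized. This takes away nearly all of the certainty and most of the high-confidence calls. It does not cure the average: with sizes near the present ones that stays at roughly 60-67%. The cost is a new list, one protocol sentence and IRB/REB approval of the revision. Eligibility, treatment, sample size and analysis are unchanged.

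**Optional, for the sponsor to weigh.** To bring the average down, replace within-center blocks by one of the following (figures for about 48 patients per center):

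- central blocks over the six clinical cells: about 50% guessable, with mean center imbalance rising from about 2 to about 5.5 patients of 48;
- a fair coin with a per-center imbalance cap of 6 or 8: 53.1% or 51.8% guessable, with mean center imbalance of about 3 or 4 of 48, and about 25 of 2354 overall.

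The price is center balance and a change to the analysis text. The Analysis of Primary Endpoint section takes its log-rank strata and Cox covariates from the randomization factors. If center leaves the randomization, that section must state whether it stays a stratum in the test and a factor in the model.
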